3.3.2 Exclusion Criteria

The following criteria will exclude a subject from participating in the study:

1. Medical history of treatment failure to any systemic agents (including biologic and non-biologic systemic agents) for plaque psoriasis;
2. Presence of erythrodermic psoriasis, pustular psoriasis, guttate psoriasis, medication-induced psoriasis or other skin conditions at (e.g., clinically-significant eczema or severe acne) that could interfere with study evaluations at Visit 1;
Note: Subjects with psoriatic arthritis will not be excluded from the study provided that criteria for cutaneous severity of psoriasis, as well as all other study restrictions required by the protocol are met.
3. Presence or history of any itch due to underlying conditions other than plaque psoriasis which cause or influence pruritus of the skin (e.g., drug induced pruritus, significant other systemic diseases with itch) within 12 months prior to Visit 1;
4. Does not meet all study restrictions, including previous/concomitant medication restriction criteria, as described in Section 3.5.4.1;
5. Leucocyte count of $<3.0 \times 10^9/L$ ($<3000/mm^3$), absolute neutrophil count of $<1.5 \times 10^9/L$ ($<1500/mm^3$) or absolute lymphocyte count $<0.8 \times 10^9/L$ ($<800/mm^3$) at Visit 1; Hemoglobin <11 g/dL or platelet count $<100,000/mm^3$ at Visit 1;
6. ALT >2.0 X the upper limit of normal (ULN) or AST >2.0 X the ULN at Visit 1;
7. Evidence of renal impairment; serum creatinine >1.5 X the ULN at Visit 1;
8. Hemoglobin A1c (HbA1c) $>8.5\%$ at Visit 1;
9. Serum triglycerides >400 mg/dL at Visit 1;
10. Positive viral serology at Visit 1 for:
 - Human immunodeficiency virus (HIV): positive HIV antibodies (Ab) or
 - Hepatitis B virus (HBV): positive total hepatitis B core (HBc) Ab or positive hepatitis B surface antigen (HBsAg) or
 - Hepatitis C virus (HCV): positive HCV Ab;
11. Positive drug of abuse test results at Visit 1;
Note: Non-abusive use of prescription drugs, according to the Investigator's judgment is permitted, provided that the concomitant medications restrictions required by the protocol are met.
12. Positive Purified Protein Derivative (PPD) test or QuantiFERON[®]-TB Gold-In-Tube test, positive chest radiographic findings for tubercle bacillus (TB) or any other evidence of active or latent TB;
 - For subjects with a history of Bacille Calmette-Guérin (BCG) vaccination or in case PPD test fails, the QuantiFERON[®]-TB Gold-In-Tube test should be performed;
 - A PPD test is considered positive if, at 48 to 72 hours of administration, the induration (not erythema) obtained is ≥ 5 mm. The reaction must be read between 48 and 72 hours after administration (a subject that does not return after 72 hours must be rescheduled for a repeat PPD test);

-
- If QuantiFERON[®]-TB Gold-In-Tube test is indeterminate, a retest is allowed if results can be obtained within the timeframe allowed between Visit 1 and Visit 2. If the retest is also indeterminate, the subject will be excluded from the study;
 - The QuantiFERON[®]-TB Gold-In-Tube test should not be performed within ≤ 4 weeks from the date of a live vaccination;
 - Subjects who have had household contact with a person with active TB are excluded, unless appropriate and documented prophylaxis for TB was administered.
13. History of live vaccination within 4 weeks prior to Visit 2 or have a live vaccination planned during the course of the study or within 6 weeks after the last dose of study drug;
 14. Have donated or received blood or blood products within 4 weeks prior to Visit 1;
 15. History of a clinically-significant infection (e.g., infection that required oral antimicrobial or antiviral therapy) within 8 weeks prior to Visit 2, except for treated urinary tract infections, which will be permitted if resolved >1 week prior to Visit 2;
 16. History of opportunistic infections or infection requiring hospitalization or parenteral antibiotic, antiviral, antifungal or antiparasitic therapy within 6 months prior to Visit 2 or history of recurrent infections or conditions predisposing subject to chronic infections (e.g., bronchiectasis, chronic osteomyelitis);
 17. History of shingles within 12 months prior to Visit 1 or known history of disseminated/complicated herpes zoster;
 18. History or presence of any lymphoproliferative disorder (e.g., Epstein Barr Virus-related lymphoproliferative disorder, lymphoma, leukemia, multiple myeloma) or signs and symptoms suggestive of current lymphatic disease, such as Hodgkin's or Non-Hodgkin's lymphoma;
 19. History of or current malignancies with the exception of adequately treated or excised non-metastatic basal cell or squamous cell carcinoma of the skin or cervical carcinoma in situ >6 months prior to Visit 1;
 20. History of organ transplantation;
 21. A history of substance abuse, drug addiction or alcoholism within 12 months prior to Visit 1. Alcoholism is defined as the consumption of more than 28 units of alcohol a week (an alcohol unit is defined as 300 mL of beer, 100 mL of wine, or 25 mL of hard liquor);
 22. History of decompensated heart failure, fluid overload, myocardial infarction, uncontrolled arterial hypertension or evidence of ischemic heart disease or other serious cardiac disease within 12 months prior to Visit 1;
-
-

[REDACTED]

[REDACTED]

[REDACTED]

[REDACTED]

29. Pregnant or nursing at Visit 1 or Visit 2 or plan to become pregnant or initiate breastfeeding during the study and within 12 weeks after the last dose of study drug;
30. Significant history of drug or other hypersensitivities per the investigator (e.g., multiple drug allergies or severe allergic reactions, including angioedema);
31. History or presence of any other clinically relevant medical condition or disease or laboratory abnormality including hepatic, renal, gastroenterologic, respiratory, cardiovascular, endocrinologic, [REDACTED], psychiatric (e.g., schizophrenia, manic-depressive disorder, treatment-resistant major depression), immunologic (e.g., immunocompromised subjects or subjects with autoimmune conditions other than psoriasis, such as type I diabetes), [REDACTED] or hematologic (e.g., sickle cell) disease that, in the opinion of the Investigator, may place the subject at unacceptable risk for study participation and may prevent the subject from completing the study (e.g., low life expectancy, high risk of non-compliance) or would interfere with the study conduct or data interpretation, according to the Investigator's judgment;
32. Cannot communicate reliably with the Investigator (including inability to complete the self-assessment questionnaires) or are unlikely to cooperate with the requirements of the study.

3.4 Removal of Subjects from the Study

A subject will not participate further in the study under the following conditions:

1. Withdrawal by Subject: subjects have the right to withdraw from the study at any time. However, if a subject withdraws consent because of experiencing an adverse event, the reason for subject termination should be documented as the adverse event.
2. Adverse Event: a clinical or biological adverse event or intercurrent condition(s), requiring study drug discontinuation, whether or not related to the study drug

If grade 3 findings (defined as severe or medically significant but not immediately life-threatening; hospitalization or prolongation of hospitalization indicated; disabling; limiting self-care activities of daily living [ADL] such as bathing, dressing, undressing, feeding self, using the toilet, taking medication, but not bedridden), according to the CTCAE²⁹, are noted in a subject, he/she must be promptly evaluated by the Investigator (including repeat tests, evaluation of the baseline parameters, concomitant medications, etc.) for potential withdrawal from the study. Every effort should be made to discuss with the study's Medical Monitor prior to final decision, unless not feasible, based on safety considerations.

Notes:

- The investigator may decide to evaluate or withdraw the subject from the study based on findings of lesser than grade 3 severity, according to his/her judgment.

3. Consistent Non-compliance with Study Drug (i.e., <80% or >120% compliance at two consecutive study visits; exceptions on a case-by-case basis may be permitted if approved by Sponsor or designee).

Note: Compliance will be evaluated at every study visit during the Treatment Period. If compliance of <80% or >120% is identified at a study visit, the Investigator or designee is to counsel the subject and ensure steps are taken to improve compliance.

4. Inclusion/Exclusion Criteria Not Met: If a subject who did not meet any of the study inclusion or exclusion criteria is identified after the randomization, the Investigator, Medical Monitor and Sponsor will review that subject profile, including the medical history, prior and current concomitant medications, physical examination, vital signs, 12-lead ECGs and clinical laboratory test results. Since such deviations are usually noted after randomization, the decision to be made is to allow the subject to continue the study or not. For such cases, an exception may be permitted on a case-by-case basis if the subject was randomized into the study due to a minor error determined to be of no clinical and/or safety risk to the subject. Some of the examples where case-by-case basis exceptions may be allowed are as follows:

-
- A subject who had a minor deviation from the inclusion/exclusion criteria defined for the efficacy evaluation purpose (e.g., inclusion criteria 1 through 6, exclusion criteria 1 through 4).
 - A subject who had a minor deviation in clinical laboratory test results from the cut-off values defined in exclusion criteria 6 through 11.
5. Protocol Violation: the subject is non-compliant with regard to this protocol (other than the withdrawal criteria 3 and 4 listed above), as determined by Sponsor or the Investigator on a case-by-case basis.
 6. Lost to Follow-up
 7. Death
 8. Study Terminated by Sponsor: the sponsor may suspend or terminate the study or part of the study at any time for any reason.
 9. Pregnancy
 10. Investigator Decision: the Investigator decides a subject should be discontinued for any reasons other than those already mentioned (actual reason must be documented by site).
 11. Other: actual reason must be documented by site.

Subjects who are removed from the study or withdraw consent to participate in the study after receiving at least one dose of study drug will be requested to complete an Early Termination Visit at which time the subject will undergo all the procedures described for Visit 6. Every effort should be made to perform the Visit 6 assessments as soon as possible after the last dose of study drug and the decision of discontinuation is made and prior to any changes made in the subject's anti-psoriasis therapy. Additionally, at approximately 4 weeks after study drug discontinuation, subject should return for a Follow-up Visit, where all procedures as described at Visit 7 should be performed.

3.5 Study Procedures

[figure not shown]

Figure 1. Planned Study Schema

-
- a. The target day for each visit after randomization will be calculated relative to the date of Randomization Visit (Visit 2) and not relative to the date of the previous visit. All visits should be performed within the windows specified in the table. Every attempt should be made to have the subject attend each visit as scheduled. The investigational site is encouraged to make a reminder phone call to the subject approximately a day or two before the scheduled visit. However, if a subject is unable to attend a visit within the specified windows, the visit should be scheduled as closely as possible to these windows. A subject should not skip a protocol-specified visit due to scheduling difficulties.
 - b. [REDACTED]
 - c. Chest radiography may not be performed if it has been performed within 12 weeks of Visit 1 and documentation is available for review by the Investigator and inclusion in the subject's file.
 - d. At Visit 1, serum pregnancy test will be performed for all female subjects. At Visits 2 through 7, urine pregnancy tests will be performed only for female subjects of child bearing potential. At Visit 1, females with a documented history of lack of menses for ≥ 12 consecutive months with no other reversible medical etiology will be considered postmenopausal. If the female is positive for lack of menses but onset has been < 12 months, then an FSH > 40 will be required to define post-menopausal status, otherwise subject is considered of childbearing potential.
 - e. Both WI-NRS and AI-NRS during a 24-hour recall period will be recorded by the subject once daily from screening through the last visit.
 - f. [REDACTED]
 - g. All subjects will be required to take photographs of the [REDACTED] four half-body views (i.e., upper anterior, lower anterior, upper posterior, and lower posterior). However, if collecting photographs is raised as the reason for not participating in the study, the subject still can be part of the study without collecting photographs. In all the photographs, subject identification will be blinded.
 - h. At Visit 2 through Visit 5, randomized subjects will receive sufficient study drug blister cards for the period between visits. At Visit 6, study drug will not be dispensed. If a study subject discontinues study drug prematurely, the termination should be recorded as soon as possible after the decision has been made.
 - i. [REDACTED]
 - j. Subjects will be instructed to bring all used and unused blister cards to each study visit for accountability purposes. Study drug compliance will be calculated by the site at each visit during the Treatment Period starting at Visit 3, based on the number of tablets dispensed to and returned by the subject.
 - k. Oral administration for 12 weeks starting on the day of randomization at Visit 2, QD in the morning, regardless of meals. On study visit days, subjects should take their scheduled study treatment from their existing study drug supply (if available) at the site, under the supervision of the investigator or designee after all study-related procedures have been performed (except for Visit 6, when no study drug will be administered, as the last dose will be taken the day prior to the visit).
 - l. See [Figure 2](#) for a detailed description of dosing and PK sampling time points.
 - m. Adverse event information will be collected at the specified time points as well as at any time when a site staff member becomes aware of an AE after the subject signs the informed consent for the study. However, stable or improving pre-existing conditions detected through the screening procedures during the Screening Period (e.g., abnormalities in ECG, physical examination, [REDACTED] vital signs and laboratory tests) are considered to be medical history and should be documented accordingly.

[figure not shown]

Figure 2. Dosing and Pharmacokinetic Sample Collection Time

- The exact date and time of dose at each visit at the site will be collected.
- The exact date and time of the last three doses prior to the PK sample collection will be collected.
- The PK samples at pre-dose point (i.e., samples obtained prior to the morning dosing of the study drug at the site) are mandatory in all subjects at all sites. Sample collection date and time will be collected.
- The PK samples at trough point (relative to dosing of the study drug at the day prior to the visit) are mandatory in all subjects at all sites. Sample collection date and time will be collected.
- Every effort should be made to collect post-dose PK samples (relative to the morning dosing of the study drug at the site) from as many subjects/treatment as possible. Sample collection date and time will be collected.
- The sampling time between post dose blocks (boxes in Figure 2) should be separated by at least 1 hour.

3.5.1 Screening Period

Day -28 (Visit 1) to Day 1 (Visit 2)

Following signature of the informed consent for the study, screening procedures to confirm eligibility may be performed across multiple days, as needed, during the Screening Period. Washout of previous medications can begin once the subject signs the informed consent regardless of the 28 day screening period. If a subject arrives for a visit not having fasted (overnight fast, at least 10 hours prior to blood and urine sample collection), all study procedures except the blood/urine collection activities may be performed; the blood/urine collection will be rescheduled on a subsequent day within the visit window and the subject will be reminded to fast overnight.

Please refer to [Table 1](#) for the list of screening procedures to be performed in the study. A one-time repeat of the screening laboratory (except for drugs of abuse and alcohol, viral serology and pregnancy tests), vital sign and ECG assessments is permitted, if considered appropriate by the Investigator, except stated otherwise (e.g., up to three-time repeat of blood pressure measurements at the Screening Visit is permitted). The repeat test(s) result(s) are to be utilized for subject qualification purposes. If the repeat test results are outside the protocol-required range, the subject should be excluded from the study.

Re-screening of subjects may be permitted on a case-by-case basis, pending discussion and approval by the Medical Monitor.

3.5.2 Double-blind Treatment Period

Day 1 (Visit 2) to Day 84 ±2 (Visit 6/Week 12)

Please refer to [Table 1](#) for the by-visit list of procedures to be performed in the study during this period.

All visits during the Double-blind Treatment Period (i.e., including Visit 2 [Randomization Visit]), should be performed under fasted conditions (overnight fast, at least 10 hours prior to blood and urine sample collection). If a subject arrives for a visit not fasted, then all study procedures except the blood/urine collection activities may be performed; the blood/urine collection will be rescheduled on a subsequent day within the visit window and the subject will be reminded to fast overnight. Exception to this would be Visit 2, at which all study procedures have to be completed within the same session, therefore, if the subject is not fasted, the full visit should be rescheduled.

All visits should be performed within the windows specified in [Table 1](#). Every attempt should be made to have the subject attend each visit as scheduled. The site is encouraged to make a reminder phone call to the subject approximately a day or two before the scheduled visit. However, if a subject is unable to attend a visit within the specified windows, the visit should be scheduled as closely as possible to these windows. A subject should not skip a protocol-specified visit due to scheduling difficulties.

Subjects will be administered the first dose of study drug at the site, upon completion of all pre-dosing procedures and randomization at Visit 2; subsequently, they will be instructed to self-administer study drug QD, in the morning, regardless of food. However, subjects should not take study drug in the morning of the day of a study visit until after all study procedures

have been completed (except for appropriate PK samples collection procedures as discussed in Figure 2). On those days, study drug will be administered at the site by the study personnel from the subject's previously supplied study drug blister cards, if available, except for Visit 6, when no study drug will be administered, as the last dose will be taken the day prior to the visit. If the subject inadvertently took study drug on the day of the study visit, prior to the visit, he/she may complete the visit and the actual date and time of the last dose prior to the PK blood samples collection will be accurately recorded.

The exact date and time of the last three doses prior to the PK sample collection and the dosing time after the initial (trough) PK sample collection at each visit during the Treatment Period (i.e., Visits 2 through 6) should be documented.

Study drug will not be administered and all remaining study drug will be collected from the subjects at Visit 6.

If a subject discontinues the study prematurely after receiving at least one dose of study drug, an Early Termination Visit should be completed at which all procedures listed for the Visit 6 should be performed, if possible, prior to any changes made in the subject's anti-psoriasis therapy.

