1.3.2 Justification for Study Design

[figure not shown]
[figure not shown]
A parallel group, placebo-controlled design will be employed in this study, to assess the effect of JTE-051 on the efficacy parameters and to evaluate the safety of JTE-051, compared to placebo in subjects with plaque psoriasis. Briefly, upon completion of all protocol-mandated screening procedures, the qualified subjects will be randomized at Visit 2 in a 1:1:1:1:1 ratio to one of the following five parallel dose groups: JTE-051 50 mg QD, JTE-051 100 mg QD, JTE-051 150 mg QD, JTE-051 200 mg QD or placebo QD (17 subjects to be randomized per arm; see Section 3.8.1.6 for considerations related to sample size calculation), and will receive the double-blind treatment for 12 weeks followed by a 4-week Follow-up Period. The single ascending dose study (AE051-U-11-001) data demonstrated no food effect on the PK of JTE-051; thus, study drug will be administered regardless of meals; nonetheless, based on the PK characteristics of the compound, the protocol requires the study drug administration in the morning to ensure an approximately 24-hour period between dosing, (see Section 1.2.2). The duration of the double-blind treatment period is sufficient to obtain proof-of-efficacy in subjects with plaque psoriasis, as an initial step in development. The duration of the Follow-up Period is set to approximately 4 weeks, standard duration for similar out-patient studies administered an investigational product. Based on the PK characteristics of JTE-051 (see Section 1.2.1), this period is considered conservative,

The efficacy parameters assessed in this study are consistent with the standards in the industry in similar psoriasis trials; appropriate efficacy analyses are planned, as detailed in Section 3.8.3.2. To minimize the chances of errors, all calculations of derived parameters will be done by the Sponsor based on the appropriate core data points collected and documented by the Investigators.

With respect to safety, adequate procedures have been implemented to minimize the risks to the study subjects (based on the compound's MOA and the nonclinical and clinical data available to date [see Sections 1.2.1, 1.2.2 for summary information and the IB for detailed information]) and to facilitate further characterization of the safety profile of JTE-051.

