3.5.6.32 Pharmacokinetic Procedures

3.5.6.32.1 BLOOD SAMPLES FOR PHARMACOKINETIC ASSESSMENTS

Blood samples for the quantification of plasma JTE-051 will be collected, according to the schedules summarized in [Table 1](#) and [Figure 2](#). Trough PK blood samples will be collected in the fasted state at pre-specified study visits.

At each study visit during the treatment period (i.e., Visits 2 through 6), the actual dosing date and time, as well as the sample collection date and time will be documented for PK data analysis (see [Figure 2](#)). Refer to the laboratory manual for specific instructions for the collection, processing, storing and shipping of blood samples for PK assessments.

[figure not shown]

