3.7.5 Administration of Study Drug

During the Treatment Period, beginning on the day of Visit 2, subjects will self-administer one dose of study drug (4 tablets) daily for 12 weeks. Study drug will be taken QD in the

morning, regardless of meals. On the scheduled study visit days, subjects should not take study drug prior to arriving to the site. At the site, study drug will be administered from the previously supplied blister card, if available, after all study procedures have been completed (except for appropriate PK samples collection procedures as discussed in [Figure 2](#)). If no tablets from the previously supplied blister cards are available, then the subject should dose from the new blister card supplied at that visit.

Randomized subjects will receive three study drug blister cards at Visits 2 and two study drug blister cards at Visit 3. Subjects will receive four blister cards each on Visits 4 and 5. The subjects will be instructed to use the blister cards on a first-in/first-out basis and to return all study drug blister cards from the former visit for accountability and compliance assessment at Visits 3, 4, 5 and 6 for accountability and compliance assessment. Following completion of accountability and compliance assessments, any unused blister card or a partially used blister card with the study drug available will be returned to the subject. At Visit 6, study drug will not be dispensed.

In the event that the subject does not take the study drug on a given day during the Treatment Period, the subject should not take more than the daily dosage on the following treatment day.

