3.8.5.1 Trough Concentration

Trough (pre-dose) plasma concentrations of JTE-051 at Weeks 2, 4, 8 and 12 will be summarized in terms of the number of subjects, arithmetic mean, standard deviation,

coefficient of variation (CV%), median, minimum and maximum by treatment and visit. The relationship between the dose and trough plasma concentrations of JTE-051 will also be assessed.

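### A subject who arrives unfasted at Visit 6 has the Week 12 trough PK sample deferred until at least 48 h after the last dose, because dosing has already ended

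*Protocol*

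**What the plan says.** Protocol 3.5.2 requires an overnight fast before every treatment-period visit. If the subject has not fasted, the other procedures may go ahead and "the blood/urine collection will be rescheduled on a subsequent day within the visit window and the subject will be reminded to fast overnight". One visit is carved out: "Exception to this would be Visit 2, at which all study procedures have to be completed within the same session", so an unfasted Visit 2 is rescheduled whole. Visit 6 has no such carve-out.

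The same section covers dosing at Visit 6. Drug is given at the site on visit days "except for Visit 6, when no study drug will be administered, as the last dose will be taken the day prior to the visit". It adds: "Study drug will not be administered and all remaining study drug will be collected from the subjects at Visit 6". Section 3.7.5 agrees: "At Visit 6, study drug will not be dispensed".

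On the PK sample, 3.5.6.32.1 states: "Trough PK blood samples will be collected in the fasted state at pre-specified study visits". The notes to Figure 2 in section 3.5 define the trough sample relative to the dose on the day before the visit and make it mandatory in all subjects. Section 3.8.5.1 plans the analysis: "Trough (pre-dose) plasma concentrations of JTE-051 at Weeks 2, 4, 8 and 12 will be summarized". It sets no limit on time since the last dose. Section 1.3.2 reports that the single ascending dose study's "data demonstrated no food effect on the PK of JTE-051".

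**The concern.** The deferral rule does little harm while dosing continues. At Visits 3 to 5 the subject can go on taking the drug, and a next-day sample can still fall about 24 h after a dose. At Visit 6 dosing has stopped and the drug has been handed back, so each day of deferral adds a day without drug. The sample would still carry the Week 12 trough label.

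PK is one of the three study objectives, and Week 12 is the last planned trough. Section 3.8.5.2 gives trough concentration as its example exposure measure for an optional exposure-response analysis against PASI 75 at EOT. A late sample reads low for a reason unrelated to dose or adherence, and the true trough cannot be recovered once dosing has ended.

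**Working it through.** The plan gives no figure to reproduce, so the check is date arithmetic.

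**Inputs**
- Visit 6 window: Day 84 ±2, that is Days 82 to 86 (Protocol 3.5.2; SAP Table 1).
- Last dose: the day before Visit 6 (Protocol 3.5.2).
- Deferred draw: a later day, inside the window (Protocol 3.5.2).
- Intended trough: about 24 h after the previous day's dose (Figure 2 notes).

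**Formula.** Let v be the Visit 6 day and d the deferred draw day, with v + 1 ≤ d ≤ 86. The last dose is on day v − 1. Assuming the same clock time for dose and draw, hours since last dose = 24 × (d − (v − 1)).

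| Visit 6 day | Last dose day | Possible deferred days | Hours since last dose |
|---|---|---|---|
| 82 | 81 | 83, 84, 85, 86 | 48, 72, 96, 120 |
| 83 | 82 | 84, 85, 86 | 48, 72, 96 |
| 84 | 83 | 85, 86 | 48, 72 |
| 85 | 84 | 86 | 48 |
| 86 | 85 | none | rule cannot be met |

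The minimum is 24 × 2 = 48 h and the maximum is 24 × (86 − 81) = 120 h, against about 24 h intended.

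**Is supply the limit?** No. Section 3.7.5 dispenses 3 + 2 + 4 + 4 = 13 cards, and 3.7.4 gives 8 days per card: 13 × 8 = 104 days against 84 days of treatment. Any surplus is collected at Visit 6, so the interruption comes from the rules and not from a shortage.

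**What the delay could do to the value.** The half-life is not in the visible text, so the following is illustrative only. Assuming first-order decline, the fraction of the 24 h trough remaining at h hours is 0.5^((h − 24)/t½).

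| Assumed t½ | At 48 h | At 72 h | At 120 h |
|---|---|---|---|
| 6 h | 6% | 0.4% | about 0% |
| 12 h | 25% | 6% | 0.4% |
| 24 h | 50% | 25% | 6% |
| 48 h | 71% | 50% | 25% |
| 96 h | 84% | 71% | 50% |

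A one-day deferral could therefore leave anything from 6% to 84% of the intended value over this assumed range. The documents do not say where in the range the drug lies.

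**The case against.** The strongest reply is that the consequence is now slight. SAP section 5 reports early termination with 13 subjects randomized, no inferential tests, and most data in listings only. SAP section 4 says the PK population will not be identified. SAP 6.1 contains no trough table, and plasma concentrations appear only in listing 16.2.5.3. This stands: no Week 12 trough mean or CV will be produced, and no exposure-response analysis is planned there.

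Mitigation was also built in, and this stands as well. The times of the last three doses and of each sample are recorded, so a late sample can be recognized and used at its actual time in the population PK analysis of 3.8.5.3. Section 3.8.1.5 requires a usable concentration, but the word is undefined and is not a timing rule. Section 3.8 calls itself abbreviated, so analysis detail could have followed later; that does not repair the collection rule in 3.5.2.

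A site could also postpone the whole visit, since the other procedures are allowed rather than required on an unfasted day. But the protocol demands this only at Visit 2. Section 3.5.2 does tolerate visits slightly outside the window, but that text concerns subjects who cannot attend, not deferred blood. Figure 2 and the laboratory manual are not available and might address Visit 6.

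Three stronger readings are tempting and unsupported:
- **Week 12 safety labs become washout values.** Fasted hematology, chemistry and urinalysis are deferred in the same way, but nothing in the documents shows them shifting over the days concerned.
- **Early Termination samples contaminate the Week 12 trough.** The protocol says Visit 6 procedures are performed at that visit. It does not say the resulting samples are pooled with Week 12.
- **Arm means fall by a stated percentage.** That needs both a half-life and a frequency of unfasted Visit 6 arrivals, and the documents give neither. Reminder calls are encouraged and every treatment-period visit is fasted, so such arrivals may be few.

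**Conclusion.** The point holds as an internal conflict in the protocol. The deferral rule, the last-dose timing and the drug collection at Visit 6, followed as written, yield a sample 48 to 120 h after the last dose where the plan intends about 24 h, and they leave a Day 86 visit with no compliant option. The timing result rests on the stated window, a last dose the day before the visit, and similar clock times. It does not depend on the half-life.

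The number of subjects affected and the bias in any summary are unknown. As the study is now to be reported, the effect is confined to the plasma concentration listing, where a late sample could be read as a trough. It is a modest point, worth correcting because the sample cannot be retaken and the remedy is short.

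**What to change.** - **Protocol 3.5.2 and 3.5.6.32.1:** state that the Visit 6 PK sample is drawn on the visit day whether or not the subject has fasted, and record fasting status. Given the reported absence of a food effect, the documents offer no PK reason to wait.
- **Safety labs:** leave the fasted tests under the existing deferral rule, flagged with time since last dose. Drawing them unfasted would lose comparability with fasted baseline values. The sponsor should also say what happens to them when Visit 6 falls on Day 86.
- **Protocol 3.8.5.1:** admit a sample to any trough summary only if its recorded time since last dose fits a once-daily trough, with the limits fixed in advance. Use the other samples at their actual times in population PK.
- **SAP listing 16.2.5.3:** show time since last dose beside each concentration.

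The cost is a few sentences and a possible second blood draw for a subject who arrives unfasted. Dose and sample times are already collected; fasting status at the draw is the only added item. Nothing here changes dosing.
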